2. STUDY SCHEDULE AND TIMELINE

IBSOS is a prospective, randomized, multi-site clinical trial comparing three types of psychotherapy delivered in an individual format for severely affected adults with IBS. After a four-week baseline data collection period, participants will be randomly assigned to receive either four-session self-administered CBT, 10-session therapist-administered CBT or a control condition emphasizing support and education (allocation 1:1:1). The acute treatment phase will last 10 weeks. Participants will undergo follow-up examinations two weeks after treatment ends (week 12) and three, six, nine, and 12 months after the end of treatment.

IBSOS requires the expeditious enrollment of a sufficient number of participants to ensure the statistical power and generalization of study results. This trial plans to recruit 480 participants over an approximately four-year treatment delivery period. Assuming a relatively conservative pre randomization dropout rate of 25%, each site will need to phone telephone screen approximately 150 participants per year and enroll (consent) 75 in order to meet yearly recruitment quotas of 60 randomized participants at each site.

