4. STUDY POPULATION

4.1 Number of Sites and Participants

The sample will consist of 480 adult (18-70 inclusive) volunteers (240 participants x two sites) who meet Rome III diagnosis of IBS. The sites were chosen partly to yield a geographically and ethnically diverse sample that is broadly representative of individuals with IBS. The IBSOS infrastructure includes the Administrative Core (CC) at the University at Buffalo (Buffalo, New York). The AC is directed by Project PI [name]. Northwestern University Feinberg School of Medicine (Chicago, Illinois), the other clinical site, is led by SI [name], who serves as vice chair of the IBSOS. The AC at UB is responsible for oversight for both clinical sites. Each clinical site is responsible for the recruitment, retention, and safety of their participants and for the acquisition and integrity of the study data.

See Appendix 3: Study Organizations

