5. ASSIGNMENT TO TREATMENT GROUPS

5.1 Randomization

Participants in the IBSOS will be randomly assigned to one of three treatments. Random assignment is important to ensure that the different experimental treatments will be given to comparable groups of participants. Treatment assignments will be generated using an existing web-based participant registration and randomization system at Frontier Science. This system uses protocol-specific specifications files to present questions to the sites to evaluate a participant for eligibility. Only participants who meet all the eligibility requirements can be randomized to the study. The participant enrollment system also collects basic demographic information at the time of enrollment. The Protocol Data Manager at Frontier Science will work with the Principal Investigator and Project Statisticians to develop these files based on the eligibility criteria of the protocol. Treatment allocation assignments are stratified by clinic site. This will ensure initial comparability between groups of eligible participants, for whom treatments are compared, thus eliminating the impact of individual and site difference variables on outcome.

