6. DESCRIPTION OF THERAPY

The IBSOS features two specific types of psychological treatment, either Education Supportive Counseling (Attention Control Condition) or Cognitive Behavior Therapy (CBT). Cognitive Behavior Therapy will be delivered in two "dosages": a home-based, self-administered version (four sessions) or a clinic-based, therapist delivered version (10 sessions). In this respect, the trial features three discrete treatment conditions:

- Ten-session, therapist-administered CBT
- Four-session, participant-administered CBT
- Four-session Attention Control Condition

The Attention Control Condition represents a credible attention-placebo condition that provides adequate control for the non-specific factors (e.g. attention from university-based medical staff and faculty) that foster improvement in participants treated with CBT. Thus, the trial will feature three treatment arms. All treatments will be manualized and conducted on an individual, outpatient basis by a highly trained therapist.

Complete explanations of these therapies can be found in the Treatment Manuals. The following section provides a brief summary of the nature, structure, and format of featured treatments:

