7.4. Formal Data Analysis

Aim 1

The primary focus of Aim 1 is to establish whether the effects of MC-CBT and S-CBT are comparable. We will pursue this from two perspectives: a traditional hypothesis testing framework and an equivalence testing framework. For the core outcome variables, we have assessments at baseline (BL), immediate post-test (FU W12) and at three-, six-, nine-, and 12-month follow-ups (FU3, FU6, FU9 and FU12) for each of three groups (MC-CBT, S-CBT and the active comparison control (attention control)). The traditional analysis for a given outcome variable is a two-way analysis of covariance

using the three groups as a between-participants factor, time as a within-participants factor (IM, FU3, FU6, FU9 and FU12) and the baseline score as a covariate. Single degree of freedom contrasts focus on the pair-wise comparisons of adjusted means within a given time period (e.g. comparing MC-CBT, S-CBT, and the attention control condition). Of interest is whether there are statistically significant pair-wise contrasts between the groups. We will pursue such contrasts using non-pooled error terms across time (because of the likely violation of sphericity), but with pooled error terms across groups within time (unless diagnostics suggest otherwise). We will use the program M Plus to estimate the single degree of freedom contrasts (by translating the analysis of covariance model into an SEM framework). M Plus has the capability to take into account cluster effects, should that be necessary, and it also offers robust algorithms.

In terms of statistical power, for a single degree of freedom contrast between two independent groups with a single covariate, the approximate sample size needed to achieve power of 0.80 for an adjusted mean difference of d = 0.50 (using Cohen's d) is approximately 65 per group. To achieve power of 0.90 requires a sample size of 85 per group. Our sample sizes easily meet these standards.

Aim 5

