Aim 5 emphasizes evaluating the long-term durability of acute treatment effects at three, six, nine, and 12 months post-treatment. Accordingly, a second type of analysis will compare the decay functions of the different groups, to determine if the decline (or improvement) in treatment effects from IM to FU12 differ depending on the type of treatment received. For example, it might be found that the beneficial effects of MC-CBT decline more rapidly than S-CBT in the months following the completion of the formal treatment regimen. This can be tested using growth curve analysis in an SEM framework. For a single outcome and a linear growth curve, the basic growth curve model is parameterized using figure 1. The three treatment groups are represented by two dummy variables. The intercept represents the score at IM and the slope represents the linear decay function. The path coefficients from the dummy variables to the latent slope variable represents group differences in the average slope characterizing the decay function. The statistical technology for executing these analyses is straightforward and well-developed ^{16, 17}. It is possible that the decay functions are nonlinear. One strategy for modeling non-linear trajectories is to use guadratic regression, but this can yield parameter estimates that are difficult to interpret or the non-linearity may not be quadratic in form. An alternative approach is to use spline regression in which meaningful spline knots are identified and then slopes are measured between knots. This approach is readily incorporated into growth curve analyses and involves representing each slope defined by knots as a distinct latent variable. We will use M Plus to estimate the parameters of the growth curve. The program has the capability to take into account cluster effects due to site, should that be necessary, and it also offers robust algorithms.

In terms of statistical power, using the power analysis methods described by Raudenbush ¹⁸, we set the duration parameter at 4, the frequency of observations at 1, the standardized effect size reflecting the ratio of the group mean difference to the standard deviation of the true change component at 0.50, the within-person variance at

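### Site stratifies the randomization but is not a term in the stated models, and the only handling of site that is offered, a cluster correction, does not work with two sites

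*Protocol*

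**What the plan says.** Section 5.1 makes site the only stated stratification factor: "Treatment allocation assignments are stratified by clinic site". It describes the result as "thus eliminating the impact of individual and site difference variables on outcome". Section 4.1 gives the sample as "240 participants x two sites". With the 1:1:1 allocation in section 2, that is 160 per arm and about 80 per arm at each site.

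Section 7.4, Aim 1, sets out the terms of the analysis of covariance, the last of them being the covariate: "using the three groups as a between-participants factor, time as a within-participants factor (IM, FU3, FU6, FU9 and FU12) and the baseline score as a". Section 7.3 lists the same terms. The power statement under Aim 1 is for two independent groups with one covariate. The growth model under Aim 5 represents treatment by two dummy variables. None of these descriptions contains site.

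Site appears in the analysis text in two places. Section 7.3 includes site clustering among the preliminary checks. Section 7.4, Aim 5, says: "The program has the capability to take into account cluster effects due to site, should that be necessary". Aim 1 has a parallel remark, "M Plus has the capability to take into account cluster effects, should that be necessary", which does not say what the clusters are. Neither says what would make the correction necessary.

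Section 6 says that all treatments are "conducted on an individual, outpatient basis by a highly trained therapist". No analysis text mentions clustering by therapist. The number of therapists, their caseloads, and whether one therapist treats in more than one arm are not given.

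**The concern.** Stratification balances site across the arms. It does not remove site differences from the outcome, so section 5.1 claims too much: site variance stays in the residual unless the model takes it out. The usual course is to analyse by the factor used to stratify, which costs one degree of freedom here.

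The protocol instead offers to treat site as a cluster. That is the wrong structure for this design. All three arms are randomized within each site, so a shift common to a site cancels from the arm contrast. A cluster-based variance would also have to be estimated from two units. If it were used, both the superiority tests and the equivalence intervals would rest on an almost arbitrary standard error.

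Therapists are a more natural source of clustering in individually delivered psychotherapy. Ignoring them can make intervals too narrow, which would favour superiority and equivalence claims alike. Whether that happens here depends on facts the protocol does not state.

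**Working it through.** **1. The protocol's own figures.** Inputs (section 7.4): SD 78 for the IBS-SS, 160 per group, 95% interval, 90% tolerance; SD 19.5 for the IBS-QOL; d = 0.50. Two-sided alpha 0.05 is assumed, because none is stated.

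- IBS-SS half-width: t(0.975, 318) × 78 × √(2/160) = 1.967 × 8.72 = 17.2. With 90% tolerance, multiplying by √(χ²(0.90, 318)/318) gives 18.0. The protocol states about 18.
- IBS-QOL half-width: 4.3, or 4.5 with tolerance. The protocol states about 4.
- Sample size for d = 0.50: 63 to 64 per group for power 0.80 (stated 65), and 85 to 86 for power 0.90 (stated 85).

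The figures reproduce, and they do so with independent observations.

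**2. Leaving site out.** If site explains a share s of the outcome variance, the half-width with site in the model is √(1 − s) times the half-width without it. Assumed s: 0 to 0.10.

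- s = 0: no change, about 17.1 (normal cut-off 1.96).
- s = 0.10: 17.1 × √0.90 = 16.2, so the interval without site is 1/√0.90 = 1.05 times as wide as it need be.

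A simulation (5,000 runs per setting, two sites, 80 per arm per site, no treatment effect) gave two-sided error of 4.4 to 5.2% without site and 5.1 to 5.6% with it. The Monte Carlo standard error is about 0.3 percentage points. Omission errs on the safe side.

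**3. Treating the two sites as clusters.** Let d₁ and d₂ be the arm differences at the two sites. With equal sizes the estimate is (d₁ + d₂)/2. The cluster-robust standard error, with the usual small-sample factor G/(G − 1) = 2, reduces to |d₁ − d₂|/2. With no treatment effect the ratio follows a t distribution on 1 degree of freedom.

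- At the cut-off 1.96: error = 1 − 2·arctan(1.96)/π = 0.30. Simulation: 29 to 31% (38 to 41% without the small-sample factor).
- Half-width at 1.96 on the IBS-SS: 5th to 95th percentile about 1 to 34, median about 11 to 12.
- With the correct cut-off, t(0.975, 1) = 12.7, the error is nominal but intervals are 12.7/1.96 = 6.5 times as wide. The median half-width is then about 71 to 77 points, beyond the margin of 50.

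The protocol does not say which cut-off would apply. Neither is usable.

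**4. Therapist clustering (every input below other than SD, n and margins is an assumption).** For therapists nested in arm, with k per arm and m = 160/k patients each, the design effect is DE = 1 + (m − 1) × ICC. The actual two-sided error is 2 × [1 − Φ(1.96/√DE)]. The half-width is t(0.975, 2k − 2) × 78 × √(2/160) × √DE, with 19.5 in place of 78 for the IBS-QOL.

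| k per arm | ICC | DE | Two-sided error | IBS-SS half-width | IBS-QOL half-width |
|---|---|---|---|---|---|
| 10 | 0.01 | 1.15 | 6.8% | 19.6 | 4.9 |
| 8 | 0.02 | 1.38 | 9.5% | 22.0 | 5.5 |
| 4 | 0.05 | 2.95 | 25.4% | 36.7 | 9.2 |
| 2 | 0.01 | 1.79 | 14.3% | 50.2 | 12.6 |
| 2 | 0.02 | 2.58 | 22.2% | 60.3 | 15.1 |

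For 4 to 10 therapists per arm, the error of each one-sided equivalence test at the margin rises from 2.5% to about 3.4 to 13%. The corrected half-widths still fit inside the margins of 50 and 14. With only two per arm they may not. If therapists are crossed with arms, the shared therapist effect cancels and only therapist-by-arm variance remains.

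**The case against.** Three objections have force.

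First, covariates are often settled in a statistical analysis plan, which is not shown, and omitting site does almost no harm to inference. That stands. The missing site term would be a small matter if the protocol did not also put forward the wrong way of handling site.

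Second, the cluster remarks are conditional and describe what the software can do. Under Aim 1, which covers the main arm contrasts, the unit is not named and could be therapist. This also stands. The failure in step 3 arises only if the option is taken up with site as the unit. But site is the only unit named anywhere, in section 7.3 and under Aim 5.

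Third, the therapist figures depend on assumed counts, ICCs and nesting. Appendix 8 (Treatment Expectancies) asks for the therapist's suitability rating before randomization, which suggests that a therapist may be linked to a participant before the arm is known and so may treat in several arms. The hint is not conclusive: the form concerns the assigned treatment, and Appendix 7 schedules it at the first treatment visit. It is enough, though, to prevent the nested case from being taken as fact.

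A reader might infer that the planned standard errors and equivalence intervals will be wrong, or too narrow. The documents do not support that. Omitting site widens intervals slightly, the site-cluster correction may never be used, and therapist inflation cannot be sized without facts the protocol does not give.

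**Conclusion.** The point holds in a limited form. The stated models leave out the stratification factor, and the only handling of site that the protocol mentions is unsound with two sites. If used, it gives about 30% false positives at 1.96, or intervals roughly 6.5 times as wide on one degree of freedom. That result follows from the two-site design with equal arm sizes and needs no assumed ICC. Omission of site alone makes intervals 0 to about 5% too wide, if site explains 0 to 10% of the variance.

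The therapist point is secondary and contingent. With 4 to 10 therapists nested per arm and ICC 0.01 to 0.05, all assumed, two-sided error would be about 7 to 25%, and equivalence would remain attainable against both margins. Under crossing, most of the inflation disappears. This is an improvement worth making at little cost. It does not show that the trial's conclusions would fail.

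**What to change.** - Enter site as a fixed effect (one degree of freedom) in every between-arm model: responder, analysis of covariance and growth.
- Delete the option to treat site as a cluster under Aim 5 and the matching check in section 7.3. Under Aim 1, name the unit meant or remove the remark.
- Amend section 5.1 to say that stratification balances site across arms and that the analysis adjusts for it.
- State whether therapists are nested in arms or treat across them, and record therapist identity for each participant.
- Add a sensitivity analysis for the primary and equivalence contrasts with a therapist random effect, or therapist-by-arm if crossed, using degrees of freedom that reflect the number of therapists.

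The cost is model wording and one variable that the sites already know. The site term will if anything narrow the intervals. The therapist analysis may widen them slightly, and by more if therapists turn out to be few and nested in arm.

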3.1 Primary Objective

Aim 1. To evaluate the efficacy of MC-CBT compared to S-CBT and attention control for IBS.

Hypothesis 1: Both MC-CBT and S-CBT are superior to attention-control on the primary endpoint of global improvement of IBS symptoms and secondary endpoints of satisfactory relief of IBS symptoms, quality of life, change in stool consistency, psychological distress, IBS symptom severity, participant satisfaction, and health care use.

Hypothesis 2: Equivalence testing will show that MC-CBT does not differ from S-CBT on primary (global IBS symptom improvement) or secondary endpoints.

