The issues involved in applying equivalence testing are well known and discussed in Wellek ¹⁵. The confidence interval approach can be easily adapted to comparing adjusted mean differences in the analysis of covariance framework described earlier, as well as comparing decay functions in the growth curve analyses. A key issue in this portion of the research is the development and specification of conceptually and empirically justifiable threshold values. For example, for the IBS-SS scale, it is commonly argued that a 50-point reduction represents the cutoff for meaningful change¹⁹. This suggests that a TV of 50, such that if the population mean difference between the treatments is between -50 and +50, then the interventions are deemed functionally equivalent. Stated more formally, if the lower limit of the relevant confidence interval for the mean difference in the sample data is greater than -50 and if the upper limit is less than +50, then the interventions are declared functionally equivalent. Our previous research with the IBS-SS yielded scores that ranged from 82 to 422 with a standard deviation of approximately 78. The estimated half-width of a 95% confidence interval for a two group mean difference with a sample size of 160 per group (using a tolerance value of 90%) is approximately 18, indicating our sample size will yield interval widths that are viable for making statements of functional equivalence for this measure. As another example, the accepted standard in the field for a clinically meaningful change on the IBS Quality of Life measure (which ranged from 15 to 92 in our previous work, with a standard deviation of 19.5) is 14 units ²⁰. If two treatments yield a population difference between -14 and 14, then they can be declared functionally equivalent. The estimated half-width of a 95% confidence interval for this measure given our sample size is approximately 4, again indicating our sample sizes can sustain this type of analysis. The statistical and methodological issues for building empirical support for threshold values can be complex and are discussed elsewhere ^{21, 22}.

Aims 2 and 3

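### The two stated equivalence thresholds (0.64 and 0.72 SD) are wider than the 0.50 SD power benchmark, equivalence does not depend on beating attention control, and the primary endpoint has no threshold

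*Protocol*

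**What the plan says.** Protocol section 3.1, Hypothesis 2, states that "Equivalence testing will show that MC-CBT does not differ from S-CBT on primary (global IBS symptom improvement) or secondary endpoints". The primary endpoint (section 3.3) is binary: responder or not on the global improvement scale.

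Section 7.4, under Equivalence Testing, requires a TV fixed in advance, treats any population difference inside ±TV as trivial, and declares equivalence when the confidence interval lies wholly inside ±TV. It calls the choice of TV the key to the method. It then gives TVs for two measures, both secondary endpoints:

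- **IBS-SS.** The starting point is that "it is commonly argued that a 50-point reduction represents the cutoff for meaningful change". From this: "This suggests that a TV of 50, such that if the population mean difference between the treatments is between -50 and +50", the treatments are equivalent. Earlier work gave "scores that ranged from 82 to 422 with a standard deviation of approximately 78".
- **IBS-QOL.** A clinically meaningful change is put at 14 units, with an SD of 19.5. "If two treatments yield a population difference between -14 and 14, then they can be declared functionally equivalent".

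For 160 per group the section gives 95% CI half-widths of about 18 and 4 and concludes that the sample size is adequate for this analysis.

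Under Aim 1, the same section bases its power for single-degree-of-freedom contrasts, which include those with attention control, on "an adjusted mean difference of d = 0.50".

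**The concern.** A difference that the plan takes as its benchmark for detection in one test is classed as trivial in the other. Both TVs come from cut-offs for meaningful change on the scale. Neither is compared with the CBT-versus-control difference that MC-CBT ought to retain. Hypothesis 1 tests each CBT arm against attention control, but the protocol does not say that an equivalence claim depends on that result.

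For the primary endpoint the problem is different: equivalence is hypothesised, but the protocol gives no rule by which to declare it, and the reassurance about sample size rests on two other scales. Section 7.4 names comparability of the two CBT formats as the main focus of Aim 1, and cost hypothesis 4B relies on MC-CBT being at least as effective as S-CBT.

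**Working it through.** **Inputs, all from the protocol.** 480 participants allocated 1:1:1, so 160 per arm (section 2). SDs of 78 and 19.5, TVs of 50 and 14, 95% CI rule, d = 0.50 (section 7.4).

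**1. The plan's own figures.**
- Sample size for d = 0.50: n = 2(1.96 + 0.84)²/0.50² ≈ 63 per group at 80% power, and 85 at 90%. The protocol says "the approximate sample size needed to achieve power of 0.80 for an adjusted mean difference of d = 0.50" "is approximately 65 per group. To achieve power of 0.90 requires a sample size of 85 per group". Reproduced within rounding.
- Half-width = t × SD × √(2/160), with t on 318 df.
  - IBS-SS: SE = 78 × √(2/160) = 8.72; half-width 17.2, or 18.0 with the stated 90% tolerance. The protocol says 18.
  - IBS-QOL: SE = 2.18; half-width 4.29. The protocol says about 4.

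This arithmetic is sound.

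**2. Thresholds against the power benchmark.**

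| | IBS-SS | IBS-QOL |
|---|---|---|
| TV / SD | 50/78 = 0.64 | 14/19.5 = 0.72 |
| d = 0.50 in points | 39 | 9.75 |
| TV as a share of that | 50/39 = 128% | 14/9.75 = 144% |
| Largest observed difference still declared equivalent (TV − half-width) | 32.8 | 9.71 |

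**3. Chance of declaring equivalence.** P = Φ((TV − half-width − true)/SE); the opposite tail is negligible for the differences below.

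- True deficit 0.50 SD:
  - IBS-SS: Φ((50 − 17.16 − 39)/8.72) = Φ(−0.71) = 24%.
  - IBS-QOL: Φ((14 − 4.29 − 9.75)/2.18) = Φ(−0.02) = 49%.
- True deficit 0.25 SD (19.5 and 4.875 points): Φ(1.53) = 94% and Φ(2.22) = 99%.
- If baseline adjustment removes variance at an assumed correlation of 0.5, the 0.50 SD figures rise to 31% and 61%.

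**4. Effect of requiring superiority to attention control.** Suppose MC-CBT equals control and S-CBT is better than both by 0.50 SD. MC-CBT then beats control significantly, in the favourable direction, at most 2.5% of the time. A conditional equivalence claim cannot be more frequent than that. Allowing for the shared MC-CBT arm, the joint probability is about 2% on either scale, against 24% and 49% without the condition.

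**5. Primary endpoint.** The protocol gives no response rate, so 40–60% in both arms is assumed. Half-width = 1.96 × √(2p(1 − p)/160) = 10.7 percentage points at p = 0.40 or 0.60, and 11.0 at p = 0.50. With no TV, no equivalence power can be computed.

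**The case against.** - **The TVs are examples.** The text introduces them as such and calls the development of TVs a key issue, and a statistical analysis plan that is not shown may contain others. This is fair as far as it goes. But 50 and 14 are worded as decision rules and carry the sample-size argument. The protocol itself demands a TV in advance, and it offers none for the endpoint that Hypothesis 2 names first.
- **Meaningful-change cut-offs are a recognised anchor.** They are. The objection here is to using them unexamined as between-group margins that exceed the plan's own power benchmark.
- **Other tests would expose the failure.** Largely true. The ordinary MC-CBT versus S-CBT contrast has about 99% power at 0.50 SD, and Hypothesis 1 compares MC-CBT with a concurrent control. A false equivalence result would usually sit beside a significant deficit and a null comparison with control. The gap is that no rule says which result governs the claim.
- **Significantly different yet equivalent.** Observed IBS-SS differences of about 17.2 to 32.8 points would be both. A reader might call this a contradiction. It is not one in itself: it can arise in any sufficiently precise trial. The fault lies in the width of the margin.

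**Conclusion.** The concern holds in a limited form. Both stated TVs exceed the d = 0.50 benchmark. Applied as written, they would declare equivalence about 24% (IBS-SS) and 49% (IBS-QOL) of the time under a true 0.50 SD deficit. No condition ties equivalence to superiority over attention control, and the primary endpoint has no TV. The percentages assume 160 evaluable participants per arm, the stated SDs, no covariate gain and the 95% CI rule.

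Two stronger readings are not supported:

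- A reader might infer that MC-CBT could be called equivalent after losing the whole treatment effect. The protocol never gives d = 0.50 as the expected CBT-versus-control effect; it is a generic benchmark for pairwise contrasts. Section 8.1 says only, without a figure, that results against active controls were less impressive than those against passive ones.
- A reader might infer that the trial's claim on its primary endpoint could be made falsely at these rates. The rates belong to two secondary scales. For the primary endpoint the fault is a missing decision rule, and its misdeclaration rate cannot be calculated.

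**What to change.** 1. **Condition the claim.** Allow an equivalence claim on an endpoint only if both MC-CBT and S-CBT are significantly better than attention control on that endpoint. This needs only wording. It does not replace a tighter margin, because MC-CBT could beat control and still fall well short of S-CBT.
2. **Reset the margins.** Do not use 50 and 14 as between-group margins. Set TVs below 0.50 SD, justified by the share of the CBT-versus-control effect to be preserved. Do not choose them from what 160 per arm can support: that route leads to about 0.36–0.40 SD, which still permits loss of 72–80% of d = 0.50 (0.36/0.50 and 0.40/0.50). Restate equivalence power at 160 per arm with an allowance for loss after randomization; the protocol quantifies dropout only before it (25%).
3. **Primary endpoint.** Either set a responder-rate TV on the same basis and state its power, or state that the MC-CBT minus S-CBT difference will be estimated with a 95% CI and equivalence will not be claimed.

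Make these changes before outcome data are seen. Waiting for unblinding is not a usable cut-off, since Appendix 9 describes the trial as unmasked, with interim data going to the monitoring board.

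**Cost.** Equivalence power becomes less favourable, and equivalence may not be claimable on some endpoints. As an illustration only, an assumed margin of 0.25 SD with no true difference gives about 21% power at 160 per arm under the 95% CI rule; 80% power would need about 337 per arm.
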